#### 7.3.1 Additional arm specific data collection: LUTS

The randomly selected man or men older than 12 years of age will be asked for consent to participate in the LUTS arm. In addition to the SOSAS repeat, groin hernia and wound questions, they will be interviewed about the presence of lower urinary tract symptoms. The severity of LUTS symptoms will be assessed using the visual prostate symptom score (VPSS) visual questionnaire (Appendix 1). VPSS is the visual analogue to the more commonly used international prostate symptom score (IPSS) questionnaire. IPSS has been validated in several studies in the diagnosis of LUTS and for use in many languages (43). VPSS evaluates patient symptoms with four pictograms. They measure pollakisuria, nocturia, urinary flow rate and life quality. Studies shows that there is significantly less alteration in responses using the VPSS, suggesting that the VPSS is useful in determining LUTS, particularly in patients with low literacy (43).

#### Uflow meter

VPSS scores are evaluated in three categories, mild, moderate and severe. Only participants with a VPSS score >17, indicating a severe LUTS will be asked to complete a questionnaire related to health seeking behaviour. Also for study participants with VPSS score >17 we aim to measure flow of urine using a portable Uroflow (Uflow) meter. An Uflow meter can measure the peak urine flow rate and detect a weak urinary flow. The peak flow rate can be used as an objective measurement for detection of LUTS. The Uflow meter is a reusable plastic shaped funnel consisting of a cup and a spout divided into three chambers. The spout has a 4.6 mm diameter aperture placed at the bottom. When fluid is poured into the cup it will start to fill the funnel as well as flowing out through the aperture. At the time inflow and outflow are equal, it will maintain a constant maximal fluid level within the funnel. The accuracy and reliability of the device seems adequate for detecting LUTS or voiding dysfunction (46).

Under assumption that the prevalence of severe LUTS is 2 %, the average household size is 5,5 persons and 65 % of the population above 12 years (8,14) we estimate that from 1873 households approximately 67 participants will be asked to use the Uflow meter and complete the questionnaire about health seeking behaviour.

#### Calculation

1,873 households x 5,5 members per household x 0,5 proportion males x 0,65 proportion >12 years x 0,02 prevalence of severe LUTS =  $\pm$  67 people.

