### 7. Methods

#### 7.1. Study design

This is a population-based, cross-sectional household survey of surgical, urological and maternal health conditions. This study will investigate the prevalence of untreated and treated surgical conditions in Sierra Leone. Participants will be recruited nationwide. The methodology is based on a cross-sectional household survey evaluating the prevalence of surgical conditions, known as the SOSAS survey (7). In addition, five topics will be investigated more in-depth to complement the previously designed SOSAS survey.

Arms Prevalence study	Lead/Co-Lead	Target population
SOSAS Repeat	[name]	Two randomly selected household individuals
Lower Urinary Tract Symptoms	[name] [name]	All men > 12 years among the two randomly selected household individuals
Groin Hernia	[name]	Two randomly selected household individuals
Wound	[name]	Two randomly selected household individuals
Maternal and perinatal health	[name] [name]	All females >12 years <50 years among the two randomly selected household individuals
Surgical volume	[name]	All household members who have had a surgical procedure in past year

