#### Calculation

$$\begin{split} n &= Z^2 \ p \ (1-p) \ / \ L^2 \\ n &= \text{sample size} \\ Z &= \text{Confidence Interval (95\% - Z is 1.96)} \\ p &= \text{Estimated proportion of the prevalence of the condition looked for} \\ L &= \text{Range excepted} \\ n &= (1.96)^2 \ x \ 0.073 \ x \ (1 - 0.073) \ / \ (0.01)^2 = 2599.6 \end{split}$$

Corrected sample = sample size x effect of population size Sierra Leone x DEFF x (1/response rate) x (1/eligible rate)

n x (1 + (n-1)/ 7,090,000) x DEFF x (1/response rate) x (1/eligible rate)

2599.6 x 1.00 x 1.3 x 1/0.95 x 1/0.95 = 3744.6 = 3745

For this section of the household study, we aim to include 3,745 individuals. In total 1,873 household visits will be needed as we are including two randomly selected individuals per household.

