#### 7.3. Sample size and sampling total

For the first part of the household survey, we need to include 10,187 individuals. The average household consists of 5.5 members; resulting in 1,852 household visits. For the second part of the survey we need less household visits as we have calculated to include 3745 individuals. These individuals are clustered as 2 per household, resulting in 1,873 household visits. Due to time and financial constraints we will maximize the household visits at 1,873. This should be sufficient for the first and second part of the survey.

A pilot study will be conducted to assess the appropriateness and utility of the design and investigate the response rate, eligible rate and use of the current small design-factor. We will also monitor the time it takes to perform the extended SOSAS repeat questionnaire. The original SOSAS questionnaire took about 30-45 minutes. In order to be successful, the new extended

questionnaire should depend on the findings of the demographics of the respondent and their surgical history and current comorbidities not last longer than 60 minutes on average.

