#### 7.2.3. Sampling of the individuals for the six arms

There are six different arms in the prevalence 2019 study. Three arms have a similar selection model and three arms only include household members under certain conditions.

3xarm (SOSAS Repeat, Hernia, Wounds) = Two randomly selected household members

1xarm (LUTS)	= Only men over the age of 12 years
1xarm (Maternal)	= Only female(s) >12 years < 50 years
1xarm (Surgical Volume)	= All household members that had a surgical procedure in the last year

Inclusion of the household individuals will be according to the 'rolling the dice once rule'. Sampling of the two individuals out of the 1,873 households starts after the determination of the household size. A random number calculator will assign two household members to be surveyed. We have chosen not to include a minimum age, as this will not give a good demographic comparison with the District Health System (DHS). If one of the selected household members is under the age of 12 years, that person needs a chaperone to assist. This can be any of the present and available household members over the age of 18 years. The two selected individuals receive the SOSAS Repeat questionnaire including additional questions on groin hernia and wounds. If a randomly selected male is > 12 years of age, he will receive the additional LUTS questionnaire. If the selected household members are no men or men less than 12 years of age, in that household no additional LUTS questionnaire will be used. If a randomly selected individual is a female >12 years <50 years she will receive the additional Maternal and Perinatal health questionnaire. Additionally, the household representative will receive questions about all of the household members that had a surgical operation in the last year. These questions may be about the two randomly selected household members and/or for any additional persons residing within the ménage that underwent surgery in the last year.

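### The forecast of 67 men for the Uflow meter and the health-seeking questionnaire counts all 5.5 household members, but only two are interviewed; the protocol's own inputs give about 24

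*Protocol*

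**What the plan says.** The forecast stands in Protocol section 7.3.1, under the Uflow meter heading: "we estimate that from 1873 households approximately 67 participants will be asked to use the Uflow meter". The same men are to answer the health-seeking questionnaire, because both steps are reserved for participants with a visual prostate symptom score (VPSS) above 17. The calculation that follows is "1,873 households x 5,5 members per household x 0,5 proportion males x 0,65 proportion >12 years x 0,02 prevalence of severe LUTS", given as roughly 67 people.

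Three places define who enters the LUTS arm, and they agree with each other:

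- The design table in section 7.1 gives the target population as "All men > 12 years among the two randomly selected household individuals".
- Section 7.2.3 says "If a randomly selected male is > 12 years of age, he will receive the additional LUTS questionnaire". It adds that a household in which no man over 12 is drawn gets no LUTS questionnaire.
- Section 7.3.1 opens with "The randomly selected man or men older than 12 years of age will be asked for consent to participate in the LUTS arm".

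The household figures come from the sample size sections. For the second part of the survey: "In total 1,873 household visits will be needed as we are including two randomly selected individuals per household". For the first part, which rests on the surgical volume arm and counts every household member: "The average household consists of 5.5 members; resulting in 1,852 household visits".

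**The concern.** A man can reach the VPSS threshold only if he is given the VPSS, and the protocol gives it only to men among the two selected members. The calculation instead counts all men over 12 living in the sampled households. The 5.5 multiplier belongs to the surgical volume arm, the only arm that covers every household member.

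Health-seeking behaviour for LUTS is named in the purpose of the study (section 1), and understanding barriers to it is one of the additional aims of the LUTS arm (section 6.2.1). The data for this come only from men above the threshold. The forecast is therefore the whole expected sample for that secondary aim, and for the Uflow measurement. If it is too high by a factor of nearly three, the team will plan tables and interpretation for a group that the fieldwork is not expected to produce.

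**Working it through.** **Inputs, all from the protocol**

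- Households visited: 1,873 (section 7.2.2, sample size for the second part; section 7.3, sampling total).
- Average household size: 5.5 (section 7.3, sampling total).
- Members interviewed per household in the second part: 2 (sections 7.1 and 7.2.3).
- Proportion male 0.5, proportion over 12 years 0.65, prevalence of severe LUTS 0.02 (section 7.3.1).
- Response rate 0.95 and eligible rate 0.95 (section 7.2.2, sample size for the second part); used only for a sensitivity figure.

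**Step 1. Reproduce the stated figure.**
1,873 x 5.5 x 0.5 x 0.65 x 0.02 = 66.96, which rounds to 67. The multiplication is right. The men it counts number 1,873 x 5.5 x 0.5 x 0.65 = about 3,348.

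**Step 2. Use the men who are actually interviewed.**
1,873 x 2 x 0.5 x 0.65 = about 1,217 men over 12.
1,217 x 0.02 = 24.3, or about 24 with severe LUTS.
Starting from the individual target ("For this section of the household study, we aim to include 3,745 individuals") gives the same: 3,745 x 0.5 x 0.65 x 0.02 = 24.3.

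**Step 3. Size of the discrepancy.**
66.96 / 24.35 = 5.5 / 2 = 2.75. The expected count is about 36% of the stated one.

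**Step 4. Sensitivity to non-response and ineligibility.**
3,745 x 0.95 x 0.95 x 0.5 x 0.65 x 0.02 = 22.0.

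**Step 5. Could chance or a different prevalence give 67?**
Binomial spread around the expected count: 1.96 x sqrt(1,217 x 0.02 x 0.98) = 9.6, so roughly 15 to 34 before any clustering. To obtain 67 cases from 1,217 men, the prevalence of severe LUTS would have to be 67 / 1,217 = 5.5%, against the 2% assumed.

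**Step 6. What it means for precision, as an illustration.**
The 95% half-width for a proportion of 50% is 1.96 x sqrt(0.25 / n). The 50% is my assumption and gives the widest interval.

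| n | Half-width, no design effect | Half-width x sqrt(1.3) |
|---|---|---|
| 67 | 12.0 points | 13.7 points |
| 24 | 20.0 points | 22.8 points |
| 22 | 20.9 points | 23.8 points |

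The last column applies the design effect of 1.3 from section 7.2.2. The protocol assumes that value for surgical conditions in general, not for this subgroup.

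**The case against.** The strongest reply is that the 67 sizes nothing. The number of households comes from the 7.3% prevalence calculation and the surgical volume calculation. The main LUTS objective, the prevalence of severe LUTS, rests on all interviewed men, about 1,217 on these inputs. Quality of life is one of the VPSS pictograms and is collected from every one of them. All of this stands. A reader might infer that the prevalence estimate or the household number is undermined; the protocol does not support that.

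A reader might also infer that a stated precision has been missed. The protocol sets no precision target for health seeking or for the Uflow results, so the half-widths above illustrate the consequence and show no missed target. Nor is uroflow a listed aim of the arm: section 6.2.1 does not name it, and section 7.3.1 presents it as a measurement.

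The corrected count is itself conditional. It assumes that each household yields two interviewed members with the population's age and sex mix. The 22 may deduct too much, because sections 7.2.2 (assignment of households) and 7.2.3 replace households that are empty, refuse, or have neither selected member available or consenting. On the other side, section 7.3.5 notes that men are more often absent, which would lower the count.

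One defence of the 67 fails. Section 7.2.2 (sample size for the second part) gives a LUTS prevalence of about 6%, and 6% of 1,217 is 73. But that figure is for LUTS, while section 7.3.1 explicitly takes 2% for severe LUTS, which is what the VPSS threshold selects.

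**Conclusion.** The forecast is wrong as written. The design in sections 7.1, 7.2.3 and 7.3.1 is expected to yield about 24 men above the threshold, with about 22 as a sensitivity figure, not 67. This holds under the protocol's own assumptions of 1,873 households, two members each, 50% male, 65% over 12 and 2% severe LUTS. No place in the protocol extends the VPSS to other household members.

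The consequence is limited to the secondary aim on health-seeking behaviour and its barriers, and to the Uflow measurement. Those results will rest on roughly a third of the men forecast.

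**What to change.** In section 7.3.1 (Uflow meter and its calculation), replace 5.5 with 2 and restate the expected number as about 24 under the stated assumptions, mentioning about 22 as a sensitivity figure if wished. Add one sentence on the resulting precision: for illustration, about +/-20 points for a 50% proportion, against +/-12 with 67, before any design effect. This costs wording only; sampling, visits and estimators stay the same.

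If the intention was to screen every man over 12 in the household, the calculation can stay, but the executive summary (Methods) and sections 7.1, 7.2.3 and 7.3.1 must be reconciled with it. That is not a wording change: it would mean about 3,348 - 1,217 = 2,131 additional men to interview.

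A reader might think of raising the number by putting the health-seeking questions to men with moderate scores as well. I do not propose it. The protocol reserves those questions for severe cases, and a pooled result would describe a different group of men.

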#### 7.3.2 Additional arm specific data collection: Groin Hernia

The two household members that are randomly selected will be included in the groin hernia arm after consent. When the questionnaire raises suspicion of a groin hernia (hard or soft mass), the enumerator will request consent to perform a physical examination of the groin area. The enumerator performing the physical examination for the hernia arm is trained to diagnose this medical condition. The enumerator is trained in the different types of groin hernias; inguinal hernia, femoral hernia and scrotal hernia. He/she is able to differentiate between a direct and indirect hernia, based on physical examination and he/she understands and recognizes the differences between a reducible, non-reducible and strangulated hernia. The enumerator will inspect and palpate the groin area of the participant. Privacy of the participant will be kept in

mind and respected by performing the physical examination in a shielded place. Physical examination will be done in a standardized way.

#### **General Inspection**

If able, ask the patient to stand (preferable). Throughout the examination, it is important to explain to the patient what you are about to do next

- Inspect the patient from the front and both sides (whilst the patient is standing)
- Note any evidence of pain (e.g. stance/grimacing)
- Note any evidence of abdominal distension (may suggest bowel obstruction)
- Look for asymmetry (left vs. right groin)
- Look for scars on the abdomen and in the groin
- Look for obvious lumps protruding from the abdomen or groin
- Look for any testicular lumps or swellings

#### Assessing a Lump

Site, Size, Shape, Colour, Contour, Consistency, Tenderness, Temperature, Tethering, Cough impulse, Bruit, Lymphadenopathy

#### **Position of Hernia**

Above and medial to the pubic tubercle: Inguinal hernia Below and lateral to the pubic tubercle: Femoral hernia Below and descending from the pubic tubercle into the scrotum: Scrotal hernia Swelling in the scrotum only; possible to come above the lump; Hydrocele

#### Reducibility / Direct vs. Indirect Inguinal Hernia / Scrotal Examination

#### To complete the examination.

Thank the patient / Allow the patient time to get re-dressed / Document the examination directly.

For quality control, this method will be validated internally by evaluating the physical examination of the first 100 selected household members in the groin hernia arm. Hereby we will validate if the verbal responses of the household member (yes or no groin lump) matches the physical examination. Consequently, we do not validate if the enumerator is able to differentiate between a groin hernia and any other palpable mass that may appear in the groin region.

The prevalence of groin hernia is most likely different for adult women, adult men and children. Therefor the results of the study will be reviewed separately for each group.

#### 7.3.3 Additional arm specific data collection: Wounds

The two household members that are randomly selected will be included in the wound arm after having given consent. The wound survey will continue if the participant has a wound at the time of interview. The wound may be of any aetiology, should at least be 5 cm in diameter or at least be one month old. The minimal limit in size is chosen to prevent including participants with minor cuts. To not exclude patients with small but deep wounds, such as those caused by

osteomyelitis, the additional inclusion criteria of a wound existing for at least one month is added. Additional consent will be asked to take four photographs: one close up of the wound, one of the affected area/limbs, one of the whole affected and contra-lateral limb or part of the body and one 3D-photo. All shots will be done in the same manner; outside, in front of a clear background, ruler next to the wound and number on a small sheet of paper in close proximity to the wound. The number on a small sheet of paper is part of a coding system whereby the photo can be traced back to the individual for the health analysis. The enumerator has disposable paper rulers, a new one is used for every examination. Gloves for the enumerator will be provided and he/she is encouraged to use them correctly.

The photographs will be taken by password protected Samsung tablets. The pictures will be shot in a way that the individual cannot be traced back; excluding identifiable body parts and/or tattoos. If inevitable at the time of the photo-shoot, during post processing the photo will be anonomyzed. The photo will be uploaded in the REDCAP software. Where possible, a 3D-photo or short video will be added to the three photographs. Photographs will be transferred and deleted from the tablets to a password-protected computer and password protected and encrypted cloud-based system.

#### Blood pressure and heart rate

After completing the survey questions we will proceed to do the blood pressure measurements. Explain to the participant that you are going to take blood pressure. You have to be very sensitive in this regard and make sure that you do not offend participants with respect to their traditions and culture.

Take the following aspects into consideration: In case men have to measure women he has to be especially respectful and avoid situations that may be culturally unacceptable. Like the rest of the interview, make sure that you are doing the measurements in a completely private place. Kindly ask the participant to remove excess clothing. Make sure that the left arm is not tightly covered for measuring the blood pressure.

#### Measurement

Use the provided Blood Pressure Instrument to measure blood pressure and heart rate.

Before starting the measurements explain to the participant that you will take blood pressure 3 times and you will wait 2-3 minutes between measurements.

The participant has to be seated with uncrossed legs and relaxed for 5 minutes before the first blood pressure reading is taken. In case the participant has been seated through the whole interview you can move to the first measurement without waiting those 5 minutes. Place the left arm of the participant slightly bent and with the palm facing upwards. Put the blood pressure cuff around the upper arm of the participant. Assure that the arm does not move and ask the person not to talk while taking the measurement.

Press the start button. Wait until the machine shows the three results: DIASTOLIC, SYSTOLIC, RATE Copy the result in REDCAP Switch off the blood pressure machine Wait for 2-3 minutes before taken the second measurement of blood pressure. Press the START button again. Take the three numbers again and copy them into REDCAP Repeat this cycle once more for the third measurement

Refer the participant to a clinic when the second AND the third measurements of blood pressure have either a diastolic (DIA) level that is higher than 90 mmHg or a systolic (SYS) level that is higher than 140 mmHg.

#### 7.3.4 Additional arm specific data collection: Maternal and Perinatal Health

Every female who is among the two randomly selected household members and who is older than 12 years of age and younger than 50 years of age will be included in the Maternal and Perinatal Health arm after consent. The selected household member(s) will undergo a verbal interview. For all women that are currently pregnant, the fundal height will be measured with a tape measure.

#### 7.3.5 Additional arm specific data collection: Surgical Volume

The household representative is the main person responsible for this part of the questionnaire. Due to the nature of the questionnaire, whereby the household representative will be interviewed first, the surgical volume related questions would come before the other arms. The household representative will be asked to provide an overview of the household members that have undergone a surgical procedure in the past year. This accounts for both major and minor procedures. Through this interview, also all household members who passed away after surgery will be identified.

When the household representative identifies a member of the household who underwent a major surgical procedure within the last year, the survey will be extended with additional questions to extracting in depth information concerning the procedure. These questions focus on the type of the surgical problem and the (type of) facility where the surgical procedure was performed. The household representative, and not the specific household member, will be responsible for completing this section of the questionnaire.

It would have been preferable to target the household member who underwent the surgical procedure but it is foreseen that a substantial part of the household members who underwent a surgical procedure in the past year will not be available for interview (e.g. work, travel). The original SOSAS study in Sierra Leone demonstrated that especially male household members are more prone to be absent during the data collection, creating a selection bias (7).

To comprehend if the household representative will be able to answer the in-depth questions reliably on behalf of the household member who had surgery, we will pre-test this approach. For validation purposes, all household members of the first 50 households that had undergone a major surgical procedure in the last year will be asked to fulfil the extended questionnaire themselves as well. The questionnaire will be presented to both the household member and the household representative separately and the answers will be compared in an internal analysis. We will use the found response difference for final analysis of all data. Furthermore, a response

difference up to 10% will be accepted. If the response difference is above the 10%, we will include a second validation pilot study. We would look into the possibility of adding an additional household member to support the household representative. Hereby we will investigate if adding an additional household member will decrease the response difference. This additional household member will be identified by the household representative, but cannot be the member that underwent the surgical procedure.

Because the data collection is based on self-reporting there are two important biases that can be identified on forehand. Firstly, the household representative will especially be susceptible to the recall bias. It is unclear if the household representative will have sufficient knowledge with regard to the type of surgical problem and the facility where the surgery was performed to be able to answer the questions. To address this, we will pre-test the questionnaire on a number of surgical patients and their 'representatives' separately to observe if the answers compare sufficiently

Secondly, there could be social desirability bias. Patients might think this study aims to identify unlawful surgical practices and might choose to not disclose particular information about surgical entities in order to protect the surgical providers.

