#### 6.6. Surgical volume

Before the EVD outbreak, there were ten consultant surgeons in the public government hospitals and an estimated twenty-six in private non-profit hospitals in Sierra Leone (41, 42). The LCoGS demonstrated that a surgical workforce density of less than 20 per 100,000 specialist surgeons, anaesthesiologists, and obstetricians correlates with lower rates of maternal survival (5). Based on this reported workforce density model, there should be an estimated minimum of 1,400 specialist surgeons, anaesthesiologists, and obstetricians for the 7 million inhabitants of Sierra Leone.

In 2012, a nationwide facility survey found that all surgical providers combined, performed 400 surgical procedures per 100,000 inhabitants in Sierra Leone. Private, non-profit facilities performed 54.0% of the surgical 'met need', compared with 39.6% by public and 6.4% by private

for-profit facilities. More than 90% of the estimated surgical need in Sierra Leone was unmet in 2012 (4).

Quantifying the national surgical volume by conducting a comprehensive household survey is a novel approach. Minor and major surgical procedures will be included and classified according to the essential surgical package (DCP3 volume 1) (1). These will provide an indication of the status of delivering surgical services in light of the universal health coverage. The suggested population perspective can help identifying post-operative outcomes and provide a broad overview of the contributions of the public and the private surgical providers.

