#### 7.2.1 Sample size survey first part

Based on the found surgical met need by Bolkan *et al.*, the expected period prevalence of major surgical procedures is 0.4% in Sierra Leone (4). This means that approximately 400 major surgeries per 100,000 population per year are performed in Sierra Leone. In the surgical volume arm, we estimate that at least twice as many minor procedures are performed. This results in an estimated prevalence (P) of major and minor surgical procedures combined of  $\pm$  1% per year. The level of precision is suggested within the range of 20% of the estimated prevalence, which allow us to apply an expected range (L) of (20% x 1% =) 0.002%.

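### The surgical volume arm sets its proxy check in the first 50 households with a major operation, but the whole survey expects about 41; type and facility questions are described for major procedures only

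*Protocol*

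**What the plan says.** The validation step is in Protocol section 7.3.5 (Surgical Volume). The household representative, not the operated member, completes the detailed questions. To test this, the protocol puts the same questions separately to "all household members of the first 50 households that had undergone a major surgical procedure in the last year" and compares the two sets of answers. It calls this a pre-test. A response difference of up to 10% is accepted. Beyond that, "If the response difference is above the 10%, we will include a second validation pilot study", and adding a second household member as support would be considered. The section also states: "We will use the found response difference for final analysis of all data". Later it mentions, without a number, a pre-test on surgical patients and their representatives.

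The expected numbers come from two other places. Section 7.2.1 (Sample size survey first part) says "the expected period prevalence of major surgical procedures is 0.4% in Sierra Leone" and, for minor procedures, "we estimate that at least twice as many minor procedures are performed". Section 7.3 (Sample size and sampling total) caps visits at 1,873 households and gives 5.5 members per household.

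On scope, section 7.3.5 has the representative list both major and minor procedures. The further questions on type of problem and facility are introduced by "When the household representative identifies a member of the household who underwent a major surgical procedure within the last year". Section 6.6 says "Minor and major surgical procedures will be included and classified according to the essential surgical package", and section 6.6.1 aims to assess public and private contributions without limiting this to major procedures.

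**The concern.** A pre-test must finish early enough to change what follows. If it needs more households with a major operation than the whole survey is expected to find, its result arrives at the end of fieldwork or never, and the 10% limit and second pilot have nothing to act on. If it instead means the first households visited, it rests on almost no operated persons. In both cases the protocol still commits to using the difference for all data.

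At stake is the reliability of the proxy answers on type of problem and facility, which feed the classification by the essential surgical package and the public/private split. The protocol itself says it is unclear whether representatives know enough to answer these questions. The second issue affects the same outputs: if the questions are asked only after a major procedure, most of the expected procedures contribute nothing to them, and the answers cannot be recovered after the survey.

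**Working it through.** **Inputs.** Major procedures 0.4% per year and minor procedures at least twice as many (section 7.2.1, Sample size survey first part); 5.5 members per household and 1,873 visits (section 7.3, Sample size and sampling total); 50 validation households and a 10% limit (section 7.3.5).

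**The plan's own figure.** With Z = 1.96, p = 0.01 and L = 0.002, Z²p(1−p)/L² = 9,508, which is 2.0% below the printed 9,702. From there 9,702 × 1.05 = 10,187 and 10,187 / 5.5 = 1,852 households, as printed. The small gap does not matter here, because the number of visits is set at 1,873.

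**Reading 1: the first 50 households with a major procedure.**
- Persons enumerated: 1,873 × 5.5 = 10,301.5.
- Expected persons with a major procedure: 10,301.5 × 0.004 = 41.2.
- Chance that a household has at least one: 1 − (1 − 0.004)^5.5 = 0.0218. Expected households: 1,873 × 0.0218 = 40.8.
- Chance of 50 or more in the whole survey, assuming independence: 8.8% for households (binomial), 10.0% for persons (binomial).
- Visits needed to expect 50 such households: 50 / 0.0218 = about 2,293, against 1,873 planned.

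**If the true rate is higher than 0.4%.** Share of the 1,873 visits needed before 50 such households are expected, 50 / {1,873 × [1 − (1 − rate)^5.5]}:

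| Major rate | Share of visits |
|---|---|
| 0.49% | 100% |
| 0.5% | 98% |
| 0.6% | 82% |
| 0.8% | 62% |

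Even at double the planned rate, most of the fieldwork is over before the result exists. These figures also assume that every operated member can be interviewed. Section 7.3.5 foresees that many will be away, and those who died cannot answer.

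**Reading 2: the first 50 households visited.** Expected persons: 50 × 5.5 × 0.004 = 1.1. Chance of none: (1 − 0.0218)^50 = 0.33.

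**Precision of the response difference.** The protocol does not define the measure, so take one agree/disagree result per person as an illustration. With a single pair the difference can only be 0% or 100%. With 41 pairs and 4 discordant (9.8%), the exact 95% interval is 2.7% to 23.1%. With 50 pairs at 10%, the normal half-width is 1.96 × √(0.1 × 0.9 / 50) = 8.3 percentage points.

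**Minor procedures.** At a 2:1 ratio the minor share is 0.8 / 1.2 = 67%, or 10,301.5 × 0.008 = about 82 procedures. If the total is held at the protocol's rounded 1%, it is 0.6 / 1.0 = 60%, or about 62 procedures.

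**The case against.** Several points against a harsher conclusion stand.

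- **National volume.** A reader might infer that the response difference would distort the estimated annual volume. The text does not support this. The validation concerns the in-depth answers for members already identified as operated on. The count comes from the earlier overview question.
- **Use of the difference.** The protocol names no method. It could mean an adjustment, a reported error rate or a sensitivity analysis, and the detail may be in an analysis plan that is not shown. What remains is that the sentence ties the analysis of all data to a quantity that will be very imprecise.
- **Feasibility.** It is tempting to say that the step cannot finish. The 0.4% is a 2012 facility figure, surgical services have since been expanded, and even at 0.4% there is a chance of about 9-10% of reaching 50. Unlikely to finish, and too late to act, is what the figures support.
- **Another safeguard.** The proxy risk is not wholly unguarded, since the same section plans a pre-test on surgical patients and their representatives. However, that pre-test has no stated size, and the 10% limit is attached to the 50-household step.
- **Minor procedures.** A reader might conclude that the sector split cannot be computed for most procedures. The questionnaire (Appendix 2) is a separate document and may ask type and facility for minor procedures as well. If it does, section 7.3.5 describes it incompletely and needs only a correction.
- **The 10% limit.** It is an operational tolerance, not a claim to be proved statistically, so the interval above shows imprecision and is not a failed test.

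**Conclusion.** The validation step does not fit the protocol's own numbers. The whole survey expects about 41 persons with a major procedure, in about 41 households, against 50 households required. Completion has a chance of about 9-10%, and not early enough for the 10% limit or the second pilot to operate. Read as the first 50 households visited, the step yields about 1 person. On neither reading is the response difference precise enough to carry into the analysis of all data. The effect is on type and facility results, not on the procedure count.

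Separately, the data collection described for minor procedures falls short of sections 6.6 and 6.6.1. Unless the questionnaire already fills the gap, the classification and sector split would rest on the 33-40% of procedures that are major.

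This assumes the 0.4% rate, the 2:1 ratio (or the rounded 1% total), 5.5 members per household and independence between households. Severity: should-fix. It concerns secondary outputs of one of six arms; the sample size, the volume count and the other arms are untouched.

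**What to change.** 1. Attach the 10% decision rule to the pre-test on surgical patients and their representatives that section 7.3.5 already plans, and complete it before fieldwork. State a reachable number of pairs and define the response difference. Correct the 50-household sentence so that it has one meaning. The cost is the effort of recruiting those pairs in the pilot and questionnaire-testing period.
2. Keep any member-representative comparison within the survey descriptive, with a confidence interval. Note that absent members, especially men, will be under-represented, a bias that section 7.3.5 itself names. Limit any adjustment for the response difference to a sensitivity analysis of the type and facility results. This costs only wording.
3. Ask type of problem and facility for every reported procedure, major or minor. That is about 82 more procedures at the 2:1 ratio, so at most about 4% of households (82 / 1,873) would have a slightly longer interview. Otherwise restrict the aims in sections 6.6 and 6.6.1 to major procedures. If the questionnaire already asks these questions, only section 7.3.5 needs amending.

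No extra households are needed.
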